### **Inclusion criteria**

Patient should fulfill all this characteristics to be included:

1-age more than 12 years old.

2-weight not less than 40 kg.

3-Moderate, sever or critical COVID-19 disease as defined by WHO.

4-PCR- confirmed patients to be Positive before inclusion.

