## **Outcomes:**

Parameters that will be assessed during hospitalization at day 0(baseline), day 3, 7, 14, 28 include:

- C-reactive protein (CRP)
- ferritin
- lactate dehydrogenase (LDH)
- D-dimer
- serum creatinine(S.Cr) and estimated creatinine clearance(CrCl)
- alanine aminotransferase (ALT), aspartate aminotransferase (AST), albumin, bilirubin

Clinical outcomes measured before & during intervention

1) Primary outcomes

- 1- 28-days mortality rate (efficacy).
- 2-PCR test results at end of hospital visit (efficacy).
- 3-precentage of patients who developed infusion related or hypersensitivity reactions during and after the end of drug infusion and reporting of any Serious and unexpected adverse events may occur that have not been previously reported with REGEN-COV use that may cause drug discontinuation (Safety).

2) Secondary outcomes

- 1-Need for invasive mechanical ventilation.
- 2- Invasive mechanical ventilation and oxygen support duration (days).
- 3- Time to clinical improvement (defined as 2 points reduction in the WHO disease ordinal progression scale(11&12) or discharge, whatever happens first)
- 4- ICU and hospitalization length of stay (days).
- 5- SOFA score(13) on day 0,3,7,14, and 28.
- 6- COVID19 WHO disease progression score(11&12) from day 0 to day 28.
- 7- Inflammatory markers including CRP, ferritin, LDH
- 8- liver and kidney functions

In addition to clinical outcomes measured before and during intervention, Vital signs, glasgow coma score (GCS),complete blood count (CBC), artierial blood gas (ABG) and prothrombin time (PT) is recorded at day0.

Patients' charactrestics(age,gender) and relevant medical and medication history and current COVID-19 treatment drugs will be recorded on admission

Duration of research will be about 6 months from Novmber 2021 to March 2022

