## **Statistical Analysis Plan (SAP):**

Intention-to-treat strategy will be used in this study. Intention-to-treat strategy will be used in this study. Statistical analysis will be achieved with SPSS, version 26.

Categorical variables will be presented as proportion and percent. Continuous variables will be presented as mean (standard deviation) for parametric data or as a median (25th-75th percentile) for non-parametric data.

Regarding baseline characteristics, Kruskal-Wallis or ANOVA test (depending on type of data and the continuous data distribution (normal or not)) will be used to compare these characteristics between the study groups. We will report the P-value for our statistical tests with level of statistical significance will be P-value  $\leq 0.05$ .

In case of existing differences in some baseline characteristics, logistic regression will be performed. This allows studying the effect of these variables on the primary outcomes of the study to exclude the effect of these confounding variables and to ensure the effect on the outcomes is due to interventions.

Regarding the outcomes, we will compare the 28-day all-cause mortality rate, result of PCR test at hospital discharge and incidence of infusion related or hypersensitivity reactions during and after the end of drug infusion (primary outcome) using the Kruskal-Wallis test with reporting the P-value.

While the secondary outcomes (hospital stay duration, icu stay duration and others) are compared using Kruskal-Wallis or ANOVA test depending on type of data and the distribution of data (normal or not)

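### Ventilation, oxygen and ICU days are compared without saying how patients never on the support, or patients who die, are counted; either natural reading can mislead

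*Combined protocol and SAP*

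**What the plan says.** Under Outcomes, secondary outcome 2 is "Invasive mechanical ventilation and oxygen support duration (days") and secondary outcome 4 is "ICU and hospitalization length of stay (days"). Secondary outcome 1, listed separately, is "Need for invasive mechanical ventilation".

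The SAP gives one rule for all of these: "the secondary outcomes (hospital stay duration, icu stay duration and others) are compared using Kruskal-Wallis or ANOVA test", the choice depending on data type and distribution. It also states: "Intention-to-treat strategy will be used in this study". It does not say how that principle applies to a duration.

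The Inclusion criteria admit "Moderate, sever or critical COVID-19 disease as defined by WHO", so some patients can be expected never to need ventilation or ICU.

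Neither section defines the analysis population for the durations, a value for a patient who never had the support, or a rule for deaths. No support-free-days, composite or competing-risk measure appears.

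**The concern.** A duration of ventilation is observed only in a patient who was ventilated, and the plan lists ventilation itself as an outcome that treatment may change. If the field is left blank for everyone else, SPSS drops those patients from Kruskal-Wallis or ANOVA. The comparison is then between subsets formed after assignment. A drug that spares the milder patients leaves its sicker, longer-stay patients in the comparison and can appear to prolong ventilation.

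Counting unsupported patients as 0 days removes that selection but leaves a second problem. A patient who dies on day 4 contributes fewer ventilator days than one who survives after two weeks, so a drug that saves lives can appear worse.

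Two analysts could each follow the SAP faithfully and report opposite directions for the same data.

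**Working it through.** The plan gives no figure for these endpoints (its sample size concerns mortality only), so there is nothing to reproduce. It also gives neither the share ventilated nor a distribution of duration. Those inputs below are assumptions.

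**1. Selection, by hand.** Take 100 patients per group and no deaths.
- Control: 40 ventilated, 20 for 6 days and 20 for 14. Total = 20×6 + 20×14 = 400 days. Mean among ventilated = 400/40 = 10. Mean over all = 400/100 = 4.0.
- Drug averts the 20 short episodes. Total = 20×14 = 280 days. Mean among ventilated = 280/20 = 14. Mean over all = 280/100 = 2.8.

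The supported-only comparison says 4 days worse; the all-patient comparison says 1.2 days better.

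**2. Selection, by simulation.** Two million patients, no deaths. Severity is standard normal and the top 40% are ventilated. Duration = exp(log 8 + 0.6 × (severity − threshold − 0.45) + N(0, 0.5)), capped at 28 days. The drug averts the mildest part of the ventilations and does nothing else.

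| Averted | Ventilated | Mean days, ventilated | Days per assigned patient |
|---|---|---|---|
| none | 40% | 10.9 | 4.36 |
| mildest 25% | 30% | 12.0 | 3.61 |
| mildest 50% | 20% | 13.6 | 2.72 |

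The last column is share × mean, for example 0.20 × 13.6 = 2.72.

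**3. Dependence on the assumptions.**
- Half the severity slope (0.3): the ventilated-only mean goes from 9.9 to 10.4 or 11.1. Still reversed, but smaller.
- Zero slope: 9.0 throughout, no shift.
- Averted cases random: the mean stays at 10.9, so a 25% to 50% cut in ventilator days is hidden, not reversed.
- Most severe cases averted: the mean falls to about 9 or 8 days, so the direction is right.

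**4. At the planned group sizes.** A separate model used groups of 53, 106 and 106, 40% ventilated in the comparators, and gamma durations with mean rising from 4 to 16 days with severity. The cocktail averted the milder half of ventilations.
- Ventilated only: 12.7 days (cocktail) against 9.9; Kruskal-Wallis P < 0.05 in about 20% of trials.
- All patients with zeros: 2.5 against 3.9; P < 0.05 in about 59%.
- No effect: about 5% either way.

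**5. Death.** The Sample Size section gives 120 deaths and 250 admissions a month: 120/250 = 48%. This is rough, because the deaths are for August to October 2021 and the admissions are the current rate. Now let the drug change only fatality among the ventilated, from 80% to 40% (assumed). Of 100 patients, 40 are ventilated; those who die have 6 ventilator days, survivors have 14, and the never-ventilated survive.
- Control: (32×6 + 8×14)/100 = 304/100 = 3.04 days per assigned patient.
- Drug: (16×6 + 24×14)/100 = 432/100 = 4.32.

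A simulation with random times (mean 6 days to death; mean 14 days ventilated, capped at 28) gives 2.8 against 4.1 over all patients. Among the ventilated it gives 7.0 against 10.3. On both readings the life-saving drug looks worse.

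**6. Ventilator-free days to day 28 on the same two hand examples.**
- Example 1: 28 − 4.0 = 24.0 for control, 28 − 2.8 = 25.2 for the drug.
- Example 5, deaths scored 0: (60×28 + 8×14)/100 = 17.92 for control, (60×28 + 24×14)/100 = 20.16 for the drug.

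Both point the right way.

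**The case against.** A reader might infer that the plan restricts these comparisons to supported patients, and so abandons intention-to-treat. The documents do not say that. The SAP is silent on the population, zero is a natural value for a patient never ventilated, and the intention-to-treat statement can be read as requiring it. That reading removes the selection problem. It does not remove the death problem, and one general sentence does not define a duration for a patient without one.

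A reader might also infer that a drug preventing ventilation will look worse. That is too strong. The direction depends on averting milder cases and on duration rising with severity.

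Three limits of scope stand. Total hospital stay exists for every patient, since all are hospitalized. Patients already on support at day 0 were not selected by treatment. And need for ventilation is a separate outcome, so a preventive effect would be visible there, though that does not correct the duration test.

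Against the remedy, ventilator-free days would overlap heavily with mortality. If 40% are ventilated with 60% to 90% fatality (assumed), only 40% × 10% = 4% to 40% × 40% = 16% of patients are ventilated survivors scoring between the extremes. This stands as a reason to tabulate the components. It is also fair that oxygen use after discharge is not described as collected.

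**Conclusion.** The point holds in conditional form. The plan tests ventilation, oxygen and ICU days without saying who enters or how deaths count, and each obvious way of filling the gap has a known failure.

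Supported-only analysis can reverse a benefit (10.9 to 12.0-13.6 days among the ventilated while days per assigned patient fall from 4.36 to 3.61-2.72) or hide it. The reversal rests on an assumed 40% ventilated, no deaths, and the mildest 25% to 50% of ventilations averted. All-patient analysis with zeros can penalise a drug that reduces deaths, a practical matter at roughly 48% implied mortality.

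The calculations cover ventilation; the same reasoning applies to ICU and oxygen days, but no size is claimed for them. These are secondary outcomes, and the 28-day mortality conclusion is unaffected.

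**What to change.** In Outcomes and in the SAP:

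- Make the between-group comparison ventilator-free and ICU-free days from day 0 to day 28 in all assigned patients. Score deaths by day 28 as 0 and survivors never on the support as 28. Compare by Kruskal-Wallis.
- Treat oxygen the same way, with a stated convention for days after discharge, for example oxygen status at discharge carried forward.
- Report durations among supported patients descriptively, without a P-value.
- Tabulate deaths, need for ventilation and durations separately by group, because the score mixes death with duration and overlaps with the mortality outcome.

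The cost is SAP wording and, for ventilation and ICU, a variable derived from outcomes already planned. Oxygen additionally needs the discharge convention. Total hospital stay needs no change on account of the selection problem.

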## **Interventions:**

Population included in this study will be assigned into 3 groups with 1:2:2 ratios to receive either antibodies cocktail or standard antiviral therapy (remdesvir, favipravir) as shown in table2 and figures 2 & 3.

Group A patients will receive REGN3048-3051(Antibodies cocktail (casirivimab and imdevimab) ) in low-dose regimen 1.2 gm (1200 mg of combined antibodies) diluted in 250 ml 0.9% sodium chloride solution as single I.V infusion over 30-60 minutes.

Group B patients will receive Remdesivir :

Day1 (loading dose): 200 mg (two 100mg vials) diluted in 500ml 0.9% sodium chloride solution infused I.V over 60 minutes

Day 2-5 or Day 2-10 (maintenance dose): 100 mg (one 100mg vial) in 250 ml 0.9% sodium chloride solution infused I.V over 30 minutes

Group C patients will receive Favipravir :

[figure not shown]
Day 1 (loading dose): 1600 mg (8 tablets) or 1800 mg (9 tablets) orally or in Ryle tube / 12 hours

Day 2-5 or day 2-10 (maintenance dose): 600 mg (3 tablets) or 800 mg (4 tablets) orally or in Ryle tube / 12 hours

[figure not shown]
Patients will be received standard of care by Physicians, Clinical pharmacist , Nurses and as guided by Egyptian COVID-19 treatment protocol.

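### If recovered remdesivir patients are kept in to finish the infusion course, hospital stay and, in part, time to clinical improvement can favour the cocktail over remdesivir with no drug effect

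*Combined protocol and SAP*

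**What the plan says.** **Regimens (Interventions).** Group A receives the cocktail "as single I.V infusion over 30-60 minutes". Group B receives remdesivir with a day 1 loading dose "diluted in 500ml 0.9% sodium chloride solution infused I.V over 60 minutes", then "Day 2-5 or Day 2-10 (maintenance dose): 100 mg (one 100mg vial", again by intravenous infusion. Group C receives favipiravir over the same days, but by mouth or tube: "600 mg (3 tablets) or 800 mg (4 tablets) orally or in Ryle tube / 12 hours". No rule is given for which patients have the 5-day and which the 10-day course.

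**Outcomes.** Secondary outcome 3 is "Time to clinical improvement (defined as 2 points reduction in the WHO disease ordinal progression scale(11&12) or discharge, whatever happens first"). Secondary outcome 4 is "ICU and hospitalization length of stay (days").

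**Analysis (Statistical Analysis Plan).** The plan states that "the secondary outcomes (hospital stay duration, icu stay duration and others) are compared using Kruskal-Wallis or ANOVA test", depending on the data. Logistic regression for baseline differences is described for the primary outcomes only.

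**Not stated anywhere.** The documents give no discharge criteria, no definition of fitness for discharge, and no statement on whether a patient may leave before the study drug course is complete.

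**The concern.** For a patient kept in hospital to complete daily infusions, the discharge date marks the later of two events: recovery and the last infusion. A cocktail patient has no such floor after day 1. Where retention happens, a difference in stay between groups A and B mixes the length of the regimen with the speed of recovery. Time to improvement carries the same mixture for patients whose clock is stopped by discharge.

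Baseline adjustment, better blinding or a rule for deaths would not remove this, because the floor comes from the regimen. What is at stake is a published statement that cocktail patients recovered or went home sooner than remdesivir patients when recovery was the same. If the reason for each late discharge is not recorded at the time, it may be impossible to recover later.

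**Working it through.** **The plan's own figure.** The only computed design figure is the total of 246 for 28-day mortality. It reproduces: a three-group ANOVA with effect size f = 0.2, alpha 0.05 and 80% power needs 244, or 246 in equal groups (power 80.4%). It has no bearing here, and no figure is given for stay or time to improvement.

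**Inputs from the documents.** Groups of 53, 106 and 106; a remdesivir course ending on day L = 5 or L = 10; Kruskal-Wallis at P ≤ 0.05; hospital mortality 120/250 = 0.48, so 0.52 survive.

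**Assumptions (not in the documents).** The time T at which a patient is ready for discharge is lognormal with median m and log-SD 0.6, the same in all groups, and the ready day is R = T rounded up. A held group B patient stays max(R, L) days. Groups A and C are not held. Survivors only are compared.

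**Step 1: who is affected.** The share of held patients whose stay is lengthened is P(R < L) = Φ(ln((L−1)/m)/0.6).

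- m = 8, L = 5: ln(4/8)/0.6 = −1.155, so 12.4%.
- m = 8, L = 10: ln(9/8)/0.6 = 0.196, so 57.8%.
- m = 12, L = 5: ln(4/12)/0.6 = −1.831, so 3.4%.
- m = 12, L = 10: ln(9/12)/0.6 = −0.479, so 31.6%.

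**Step 2: days added.** The mean addition is the sum over k = 1 to L−1 of Φ(ln(k/m)/0.6).

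- m = 8, L = 5: 0.0003 + 0.0104 + 0.0511 + 0.1240 = 0.19 days.
- m = 8, L = 10: 0.186 + 0.2167 + 0.3158 + 0.4119 + 0.5000 + 0.5778 = 2.21 days.
- m = 8, half of courses 10-day: (0.186 + 2.208)/2 = 1.20 days.
- m = 12: the same sum gives 0.05 days (L = 5) and 0.99 days (L = 10).

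If only half of group B is held, halve these.

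**Step 3: rejection rate with no drug effect (simulation, nominal 5%).** With no one held, the rate is about 5%.

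| Outcome and scenario | All 5-day | Half 10-day | All 10-day |
|---|---|---|---|
| Stay, m = 8, all of B held | 6% | 42–46% | 94–95% |
| Stay, m = 8, half of B held | 5% | 13% | 39% |
| Stay, m = 12, all held | 5% | 8% | 18% |
| Stay, m = 8, all held, deaths included with the same time to death in every group | 5% | 25% | 68% |
| Time to improvement, m = 8, all held, half reach the 2-point fall first | 5% | 14% | 36% |
| Time to improvement, m = 8, all held, 80% reach it first | 5% | 6% | 9% |

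The figures are rounded; repeat runs differed by a few points (42% and 46% for one scenario).

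**Step 4: direction.** A three-group test has no direction, so groups A and B were also compared by Mann-Whitney, in a variant without the survivor restriction. With median readiness day 5, half of B held and half of courses 10-day, A versus B rejected in 65.1% of trials, and effectively every rejection favoured the cocktail.

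**Step 5: limit for outcome 3.** If every patient reaches the 2-point fall before being ready for discharge, the rate returns to about 5%.

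**The case against.** **Retention is not in the documents.** The Interventions section gives an infusion schedule, and the Population section says participants are inpatients. A reader might infer that a recovered remdesivir patient must stay until the last infusion. Nothing says so. This stands: the effect is conditional, and the high rates belong to complete retention.

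**Outcome 3 does not simply end at discharge.** A reader might take both outcomes to stop at discharge in every patient. The definition has two limbs, and holding has no effect on a patient who falls 2 points first. This also stands: the effect is smaller there and can vanish.

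**Readiness may be late.** The patients have moderate, severe or critical disease in a hospital with about 120 deaths per 250 monthly admissions. Late recovery is plausible and shrinks the effect, as the day 12 row shows.

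**Survivors only is an assumption.** The analysis plan states intention to treat and does not restrict durations to survivors. Including deaths lowers the rates but does not remove the effect when many courses run to day 10.

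**Stay is a legitimate outcome.** The Outcomes section labels its primary outcomes as efficacy or safety but gives the secondary outcomes no such label. A shorter stay because treatment is one infusion is a real consequence of that regimen. This stands for resource use. It does not support reading the difference as faster recovery.

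**The comparison is with remdesivir only.** A reader might infer an advantage over both comparators. Favipiravir is oral or by tube and may hold nobody in hospital. The planned test is also a three-group test with no pairwise follow-up described, so any direction would be read from the group summaries.

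None of these points offsets the mechanism: nothing in the plan separates drug-related stay from recovery.

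**Conclusion.** The point holds in conditional form. A single infusion is set against an intravenous course to day 5 or day 10, and discharge ends one outcome and part of another. If some recovered remdesivir patients are kept in to finish, the unadjusted comparison can favour the cocktail over remdesivir with identical recovery.

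The size cannot be fixed from the documents. For stay it ranges from nothing (all 5-day courses with late recovery, or little retention) to near-certain rejection (all 10-day courses, everyone held, median readiness day 8). It depends on the share held, the split between 5- and 10-day courses, the readiness time and the handling of deaths, none of which the plan gives. For time to improvement it also depends on how many patients reach the 2-point fall before discharge.

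It would be wrong to conclude that the two outcomes are certainly biased, or that 28-day mortality is touched; this mechanism does not reach mortality. It concerns hospital days, not ICU days, which do not end at discharge from hospital. The matter is worth correcting because the remedy is cheap and a difference in stay cannot otherwise be interpreted.

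**What to change.** Add two fields to the electronic CRF for all three groups:

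- the date the patient was *clinically fit for discharge apart from completing study drug*;
- a yes/no item, *stay prolonged only to complete study drug*.

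In the Outcomes and Statistical Analysis Plan sections:

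- Keep the actual discharge date, and report actual length of stay as resource use, not as evidence of drug efficacy.
- For hospital stay and for the discharge limb of secondary outcome 3, present the analysis using the fit-for-discharge date beside the one using actual discharge. Draw an efficacy conclusion only if the two agree.
- Report the number with prolonged stay in each group. If few patients were held, this will show it.

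**Cost.** Two data fields, one extra analysis and some reworded text. The fit-for-discharge date is a staff judgement, and the Method section describes a single-blind, non-randomised study without saying who is blinded. The date should therefore be labelled as a judgement and should not replace the objective discharge date. No change to course length or discharge practice is proposed.

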## **Aim of the study:**

1-To evaluate the efficacy of antibodies cocktail (casirivimab and imdevimab) compared to standard antiviral therapy in reducing 28-day mortality in hospitalized patients with moderate, severe or critical COVID19

2-To evaluate safety of antibodies cocktail (casirivimab and imdevimab) compared to standard antiviral therapy by monitoring of hypersensitivity and infusion related reactions or other significant adverse effects

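### Liver and kidney outcomes have no per-patient count of marked abnormalities, and the rank test that skewed values would receive hardly registers toxicity in a minority of patients

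*Combined protocol and SAP*

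**What the plan says.** The second aim of the study is a safety comparison of the antibody cocktail with standard antiviral therapy "by monitoring of hypersensitivity and infusion related reactions or other significant adverse effects".

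The Outcomes section opens its laboratory list with "Parameters that will be assessed during hospitalization at day 0(baseline), day 3, 7, 14, 28 include". The list includes "serum creatinine(S.Cr) and estimated creatinine clearance(CrCl") and "alanine aminotransferase (ALT), aspartate aminotransferase (AST), albumin, bilirubin". Secondary outcome 8 then reads only "liver and kidney functions". It gives no threshold, grade, change from day 0 or worst value.

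The Statistical Analysis Plan names hospital and ICU stay as secondary outcomes and covers the rest with a catch-all. These outcomes "are compared using Kruskal-Wallis or ANOVA test depending on type of data and the distribution of data (normal or not"). For presentation, "Continuous variables will be presented as mean (standard deviation) for parametric data or as a median" with quartiles when the data are not normal. Categorical variables get proportions, but no categorical liver or kidney variable is defined.

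The other possible route is primary outcome 3, which reports serious and unexpected events not yet known for REGEN-COV. It is tied to one of the three drugs and gives no laboratory criterion.

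**The concern.** Drug injury to the liver or kidney usually shows as a large rise in a few patients, not as a shift of the whole group. A rank test records only that those few patients are at the top, not how far above the others they are, and the median barely changes. Liver enzymes and creatinine are usually skewed, so the SAP's own rule would tend to send them to exactly these tools.

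At stake is the second aim. An arm could contain several patients with marked toxicity while the planned table shows similar medians and a non-significant p-value. The data that would reveal it are already collected, including each patient's own day-0 value. These laboratory values are also one of the few objective measures shared by all three arms. Infusion reactions cannot arise from favipiravir, which is given orally or by tube.

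**Working it through.** **The plan's own figure.** The documents give no sample size or power for liver or kidney safety. The only calculation, 246 patients for 28-day mortality, reproduces as a three-group ANOVA with Cohen's f = 0.2 and alpha 0.05 (82 per group, power 0.804). It has no bearing on this point.

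**Inputs from the documents.** Groups of 53, 106 and 106 (Table 2 and Sample Size; the 2:1:1 ratio under Population does not match these and needs reconciling, but does not alter the conclusion). Significance at 0.05. Four post-baseline visits (days 3, 7, 14, 28).

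**Assumed inputs, none from the documents.** ALT median 40; between-patient log-SD 0.6; log-SD σ of a patient's change from day 0 of 0.3, 0.5 or 0.7; 10% of one arm has a 5-fold rise at one visit; a count threshold of 3 times day 0, used only for the calculation.

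**Step 1: why ranks are insensitive.** Suppose 10% of an arm lies above every other patient, however far above.
- Probability that a patient from this arm exceeds one from another arm: 0.9 × 0.5 + 0.1 × 1 = 0.55, against 0.50 under no effect. This is the ceiling.
- The arm's median sits at the 0.5/0.9 = 0.556 quantile of its unaffected patients. With log-SD 0.6 the ratio is exp(0.6 × 0.140) = 1.09, so a median of 40 becomes about 43.5.

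**Step 2: why means differ.** With 10% of the arm raised 5-fold, its mean is multiplied by 1 + 4 × 0.10 = 1.4; raised 10-fold, by 1 + 9 × 0.10 = 1.9. The mean does move.

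**Step 3: what the count would see.** An unaffected patient reaches 3 times day 0 at one visit with probability b = 1 − Φ(ln 3/σ), and at any of four independent visits with probability 1 − (1 − b)⁴. An affected patient reaches it at the raised visit with probability Φ(ln(5/3)/σ), plus the chance from the other three visits.

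| σ | b, one visit | Unaffected, worst of four | Affected, worst of four | Affected arm: 0.9 × unaffected + 0.1 × affected |
|---|---|---|---|---|
| 0.3 | 0.0001 | 0.0005 | 0.956 | 0.096 |
| 0.5 | 0.0140 | 0.055 | 0.853 | 0.135 |
| 0.7 | 0.0583 | 0.213 | 0.805 | 0.273 |

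The contrast shrinks from about 9.6 points on almost no background (σ = 0.3), through 13.5% against 5.5% (σ = 0.5), to 27.3% against 21.3% (σ = 0.7). Noise raises the background and dilutes the signal.

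**Step 4: simulated detection at 53/106/106, 10% of one arm affected.**

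| Analysis | Share of trials with p ≤ 0.05 |
|---|---|
| Kruskal-Wallis, one fixed visit | 5-8% |
| Kruskal-Wallis, worst of four values | 10-17% |
| ANOVA on raw worst of four values, across σ | 14-53% |
| Share reaching 3 times day 0, worst of four, σ = 0.7 | 15-22% |
| Same, σ = 0.5 | 43-58% |
| Same, σ = 0.3 | 96-99% |

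The figures move by a few points with the assumed correlation between visits. With correlation 0 or 0.5, another run gave 13-18% for the count at σ = 0.7 and 42-53% at σ = 0.5; at σ = 0.7, raw ANOVA gave 14-19%, no worse than the count.

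**Step 5: limits from group A.** Ten percent of 53 is about 5 patients. For toxicity with a true rate of 2%, the chance of seeing even one case is 1 − 0.98⁵³ = 0.66. As an illustration with assumed counts, 5/53 against 3/106 is a difference of 9.4% − 2.8% = 6.6 points, with standard error √(0.094 × 0.906/53 + 0.028 × 0.972/106) = 0.043 and a 95% interval of about −2 to 15 points.

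**The case against.** The strongest reply is that the gain is smaller and less certain than it looks.

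- **Means.** A reader might infer that neither of the planned tests can see minority toxicity. That does not hold: ANOVA on raw values is clearly more sensitive than ranks and equals or exceeds the count at the noisy end. Only the rank and median path supports the point.
- **Size of the gain.** With a single post-baseline value, the count detects 35-81% at σ of 0.7 to 0.5. A reader might apply that to a worst-value rule. It does not carry over, because four chances to exceed the threshold raise the background from 1.4-5.8% to about 5-21%.
- **What the SAP commits to.** It does not say that raw values will be tested; change or categories are not excluded, and the Outcomes section does not label outcome 8 as safety. The documents support saying that the outcome is undefined and falls under a rank or mean comparison by default, not that a particular wrong analysis was chosen.
- **Reporting.** Nothing in the plan says that a non-significant test will be reported as no toxicity. That is a risk of the default, not a stated intention. Serious-event reporting may also catch some cases, although its wording is narrow.
- **Bias in a worst value.** Sampling is in hospital, and the Sample Size section's own figures imply about 120/250 = 48% mortality. The number of values per patient therefore depends on survival and length of stay, which are themselves compared. The Method section also calls the study non-RCT, while Population says patients are randomized. A crude risk difference in worst values is thus not a clean comparison.

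All of this stands and limits the claim. None of it supplies the missing per-patient count.

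**Conclusion.** The point holds for the rank and median path. Outcome 8 has no planned summary that shows how many patients in each arm had a marked liver or kidney abnormality, although the data allow it. Under the stated assumptions Kruskal-Wallis finds a 5-fold rise in 10% of one arm in about 5-17% of trials, little above the 5% error rate at the lower end. A worst-of-four count finds it in about 15-22%, 43-58% or over 95%, depending on within-patient noise.

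The power figures rest wholly on assumed laboratory variability and an assumed one-visit rise. They show direction and range, and are not a forecast for this trial. The rank ceiling of 0.55 depends only on the affected share of 10%, whatever the size of the rise. The stronger readings, that means are also blind or that the plan has no route at all to such events, are not supported. This is a worthwhile, inexpensive improvement to the safety analysis; it does not affect the primary efficacy comparison.

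**What to change.** Add to the SAP, for outcome 8:

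1. For each arm, the number and percent of patients whose worst value after day 0 exceeds a multiple of their own day-0 value, separately for ALT/AST, bilirubin and creatinine. The sponsor sets the multiples before analysis; the 3-fold figure above was only a calculation input.
2. Risk differences with 95% confidence intervals for A against B and A against C.
3. The number of patients and of measurements contributing in each arm, because sampling ends with discharge or death.
4. The same count at day 3 and at day 7 alone, so that the comparison does not rest on unequal numbers of measurements. These visits are less exposed to differences in survival and stay, though not free of them.
5. A statement that a non-significant rank test will not be read as absence of liver or kidney toxicity.

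The planned comparison of values can stay as a descriptive addition.

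The cost is a few derived variables and a paragraph of SAP text, with no new data and no change to treatment. Intervals will be wide with 53 patients in group A, so for rare toxicity the result remains mainly descriptive.
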